Appendix 7.1. Management Principles for Gastrointestinal Adverse Events

Inflammatory causes of disease should be excluded. Opioids/anesthetics may mask the symptoms of perforation. Do not use infliximab in the case of perforation/sepsis.

Diarrhea/Colorectitis Grade (NCICTCAEv4)	Handling	Follow-Up
Grade 1 Diarrhea: Defecation frequency exceeds baseline by < 4 times/day; Colitis: no symptom.	
 Continue the immunotherapy according to the study protocol; Symptomatic treatment. 	
 Closely monitor aggravated symptoms. Educate subjects to report aggravated symptoms immediately. 
If it is aggravated:
 
 Provide treatment according to the method for grade 2 or grade 3/4 situations.
Grade 2-3 Diarrhea (Grade 2): Defecation frequency exceeds baseline for 4-6 times/day; intravenous infusion of < 24 h is required; daily living is not affected; Colitis (Grade 2): abdominal pain; hematochezia. Diarrhea (Grade 3): Defecation frequency exceeds baseline for ≥ 7 times/day; fecal incontinence; intravenous infusion of ≥ 24 h is required; daily living is affected; Colitis (Grade 3): severe abdominal pain; indications for medical intervention; peritoneal signs;	
 Delay the immunotherapy according to the study protocol; Symptomatic treatment. 	
If it is improved to Grade 1:
 
 Resume the immunotherapy according to the study protocol. 
If it lasts for > 5-7 days or relapses:
 
 Intravenous administration of 0.5-1.0 mg/kg/d methylprednisolone or an equivalent orally administrated dose; When the symptoms improve to grade 1, reduce the dose of steroids for at least 1 month and consider prophylactic antibiotics to prevent opportunistic infections, then resume the immunotherapy as per study protocol. 
If the symptoms aggravated or persisted after > 3-5 days of oral administration of steroids:
 
 Provide treatment according to the method for grade 3/4 situations.
Grade 4 Grade 4: life-threatening; perforation.	
 Terminate the immunotherapy according to the study protocol; Intravenous administration of 1.0-2.0 mg/kg/d methylprednisolone or an equivalent IV dose; Add prophylactic antibiotics to prevent opportunistic infections; Consider lower GI endoscopy. 	
If symptoms improve:
 
 Continue steroid treatment until the symptoms return to grade 1, then gradually reduce the dose of steroids for at least 1 month. 
If it lasts for > 3-5 days or relapses after improvement:
 
 Add 5 mg/kg infliximab (if there are no contraindications). Note: Do not use infliximab in the case of perforation/sepsis.

Once a subject given intravenous injections of steroids shows a sustained clinical improvement, the subject can switch to an equivalent dose of oral corticosteroids (e.g., prednisone) by the time or before the dose of steroid injections starts to be gradually reduced. When switching to oral corticosteroids with an equivalent dose, it should be considered that the bioavailability of oral corticosteroids is relatively low.

Appendix 7.2 Management Principles for Pulmonary Adverse Events

Inflammatory causes of disease should be excluded. If it is due to a non-inflammatory cause, a symptomatic treatment should be given while the immunotherapy should be continued. Imaging evaluation and consultations with the respiratory department should be performed.

Grade of Pulmonitis (NCICTCAEv4)	Handling	Follow-Up
Grade 1 Only radiographic changes	
 Consider delaying the immunotherapy; Monitor symptoms every 2-3 days; Consider consulting with respirologist and infectious diseases specialist. 	
 Repeat imaging examinations at least every 3 weeks. 
If it is aggravated:
 
 Provide treatment according to the method for grade 2 or grade 3/4 situations.
Grade 2 Mild to moderate new symptoms	
 Delay the immunotherapy according to the study protocol; Consult with respirologist and infectious diseases specialist; Intravenous administration of 1.0 mg/kg/d methylprednisolone or an equivalent orally administrated dose; Consider bronchoscopy and lung biopsy. 	
 Repeat imaging examinations every 1-3 days. 
If symptoms improve:
 
 When symptoms return to near baseline levels, reduce the dose of steroids for at least 1 month and then resume the immunotherapy as per study protocol while considering prophylactic antibiotics. 
If the symptoms are not improved or aggravated after 2 weeks:
 
 Provide treatment according to the method for grade 3/4 situations.
Grade 3-4 Severe new symptoms; new onset/aggravation of hypoxia; life-threatening.	
 Terminate the immunotherapy according to the study protocol; Consult with respirologist and infectious diseases specialist; Intravenous administration of 2-4 mg/kg/d methylprednisolone or an equivalent IV dose; Add prophylactic antibiotics to prevent opportunistic infections; Consider bronchoscopy and lung biopsy. 	
If symptoms improve to the baseline level:
 
 Gradually reduce the dose of steroids for at least 6 weeks. 
If the symptoms are not improved or aggravated after 48 h:
 
 Add other immunosuppressants (e.g., infliximab, cyclophosphamide, intravenous immunoglobulin or mycophenolate mofetil).

Once a subject given intravenous injections of steroids shows a sustained clinical improvement, the subject can switch to an equivalent dose of oral corticosteroids (e.g., prednisone) by the time or before the dose of steroid injections starts to be gradually reduced. When switching to oral corticosteroids with an equivalent dose, it should be considered that the bioavailability of oral corticosteroids is relatively low.

Appendix 7.3. Management Principles for Hepatic Adverse Events

Non-inflammatory causes of disease should be excluded. If it is due to a non-inflammatory cause, a symptomatic treatment should be given while the immunotherapy should be continued. Consider imaging examinations to rule out obstruction/tumor progression.

Elevation Grade in the Hepatic Function Test (NCICTCAEv4)	Handling	Follow-Up
Grade 1 AST/ALT > 3 × ULN and/or TBIL > 1 × ULN but ≤ 1.5 × ULN	
 Continue the immunotherapy according to the study protocol. 	
 Continue hepatic function monitoring as per study protocol. 
If it is aggravated:
 
 Provide treatment according to the method for grade 2 or grade 3/4 situations.
Grade 2 AST/ALT > 3 × ULN, but ≤ 5 × ULN and/or TBIL > 1.5 × ULN but ≤ 3 × ULN	
 Delay the immunotherapy according to the study protocol; Increase the monitoring frequency to once every 3 days. 	
If symptoms recover to the baseline level:
 
 Resume routine monitoring and resume the immunotherapy according to the study protocol. 
If elevation persists for > 5-7 days or aggravates:
 
 Intravenous administration of 0.5-1 mg/kg/d methylprednisolone or an equivalent orally administrated dose. If LFT recovers to Grade 1 or to the baseline level, reduce the dose of steroids for at least 1 month, and consider prophylactic antibiotics to prevent opportunistic infection and then resume the immunotherapy according to study protocol.
Grade 3-4 ALT/AST > 5 × ULN and/or TBIL > 3 × ULN	
 Terminate the immunotherapy according to the study protocol*; Increase the monitoring frequency to once every 1-2 days; Intravenous administration of 1.0-2.0 mg/kg/d methylprednisolone or an equivalent dose via intravenous injection**; Add prophylactic antibiotics to prevent opportunistic infections; Consultation with the gastroenterology department. 	
If it recovers to Grade 2:
 
 Reduce the dose of steroids for at least 1 month. 
If not improving, or even aggravating or recurring after > 3-5 days:
 
 Add 1 g of mycophenolate mofetil, bid; If the symptoms are not relieved within 3-5 days, other immunosuppressants are considered based on local guidelines.

Once a subject given intravenous injections of steroids shows a sustained clinical improvement, the subject can switch to an equivalent dose of oral corticosteroids (e.g., prednisone) by the time or before the dose of steroid injections starts to be gradually reduced. When switching to oral corticosteroids with an equivalent dose, it should be considered that the bioavailability of oral corticosteroids is relatively low.

* If AST/ALT ≤ 8 × ULN and TBIL ≤ 5 × ULN, the immunotherapy can be delayed rather than discontinued.

**For grade 4 hepatitis, the recommended starting dose of methylprednisolone via intravenous injection is 2 mg/kg/d.

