10.1.6 Dose modifications and delay

10.1.6.1 Dose modifications for SHR-1210

Adverse events related to SHR-1210 may be immune-related (irAE), and may develop shortly after the first dose or months after the last dose. SHR-1210 should be interrupted if events listed in [Table 4](#) occur. During the study, the investigator must consult with the sponsor if, based on the benefit to risk ratio of the subject, SHR-1210 should be interrupted or resumed instead of the recommendations found in [Table 4](#) or when the situation is not listed.

When SHR-1210 is discontinued and apatinib is well tolerated, the subject may receive apatinib monotherapy.

Table 4. Criteria for SHR-1210 dose modifications

Treatment-Related Immune-Related Adverse Events (irAEs)	Severity Grades for Treatment Interruption	Resumption	Discontinuation
Diarrhea/Colitis	2-3	Recovered to Grade 0-1	Fail to resolve within 12 weeks from the last dose, or the dose of corticosteroids cannot be reduced to ≤ 10 mg of prednisone or equivalent within 12 weeks.
	4	Discontinuation	Discontinuation
AST, ALT, or bilirubin increased	2	Recovered to Grade 0-1	Fail to resolve within 12 weeks from the last dose.
	3-4	Discontinuation	Discontinuation
Hyperthyroidism	3	Recovered to Grade 0-1	Fail to resolve within 12 weeks from the last dose, or the dose of corticosteroids cannot be reduced to ≤ 10 mg of prednisone or equivalent within 12 weeks.
	4	Discontinuation	Discontinuation
Hypothyroidism	2-4	Treatment can be continued after starting thyroxine replacement therapy	Treatment can be continued after starting thyroxine replacement therapy

Treatment-Related Immune-Related Adverse Events (irAEs)	Severity Grades for Treatment Interruption	Resumption	Discontinuation
Pulmonitis	2	Recovered to Grade 0-1	Fail to resolve within 12 weeks from the last dose, or the dose of corticosteroids cannot be reduced to ≤ 10 mg of prednisone or equivalent within 12 weeks.
	3-4	Discontinuation	Discontinuation
Immune-Related Hypophysitis	2-3	Recovered to Grade 0-1; SHR-1210 treatment can be resumed after starting hormone replacement therapy	Fail to resolve within 12 weeks from the last dose, or the dose of corticosteroids cannot be reduced to ≤ 10 mg of prednisone or equivalent within 12 weeks.
	4	Discontinuation	Discontinuation

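### Appendix 7.3: the Grade 1 AST/ALT limit contains the whole of Grades 2 and 3-4, so one value meets opposing instructions on SHR-1210; the footnote also differs from Table 4

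*Protocol*

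**What the plan says.** The liver table in Protocol Appendix 7.3 has three rows, under a column header that cites NCI CTCAE v4:

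- Grade 1: "AST/ALT > 3 × ULN and/or TBIL > 1 × ULN", followed by a ceiling of 1.5 × ULN on bilirubin, with the handling "Continue the immunotherapy according to the study protocol".
- "Grade 2 AST/ALT > 3 × ULN, but ≤ 5 × ULN and/or TBIL > 1.5 × ULN but ≤ 3 × ULN", with the handling "Delay the immunotherapy according to the study protocol".
- "Grade 3-4 ALT/AST > 5 × ULN and/or TBIL > 3 × ULN", with the handling to terminate immunotherapy. A footnote permits delay instead of discontinuation when AST/ALT is at most 8 × ULN and bilirubin at most 5 × ULN.

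The Grade 2 row also covers resumption. After steroids have been given, immunotherapy may restart once liver tests are back to Grade 1 or baseline and the steroid has been tapered.

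In the main text, Table 4 (Section 10.1.6.1) has a row for "AST, ALT, or bilirubin increased". It interrupts SHR-1210 at Grade 2, resumes it on recovery to Grade 0-1, and discontinues it at Grade 3-4. It gives no × ULN limits. Section 10.1.6.2.1 directs the reader to Appendix 7 for the safety management rules. The introduction to Appendix 7 describes its principles as reference for the investigator. Section 13.1.2 grades adverse events by NCI-CTCAE v4.03.

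**The concern.** A graded management table works only if each laboratory value falls in one row. Here the AST/ALT limit for Grade 1 starts where Grade 2 starts and has no ceiling, so the row that says continue also covers the values for which the next two rows say delay or terminate. An investigator holding one laboratory result could follow either of two printed rows and be compliant with the appendix.

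The fault reaches resumption too. If Grade 1 is read from this table, an AST/ALT that stays at 4 × ULN already counts as recovered to Grade 1.

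The table matters because, within the SHR-1210 management text, it is the only place where the hepatic grades are given as multiples of ULN. Liver enzyme rises are also an expected toxicity: Protocol Section 5.3 lists treatment-related AST increase in 21.7% and ALT increase in 18.6% of 258 subjects.

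**Working it through.** No sample size, power or alpha figure is involved. The check writes the printed limits as intervals and compares them.

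**Step 1. Limits as printed (× ULN), Appendix 7.3.**

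| Row | AST/ALT | TBIL | Instruction |
|---|---|---|---|
| Grade 1 | (3, ∞) | (1, 1.5] | continue |
| Grade 2 | (3, 5] | (1.5, 3] | delay |
| Grade 3-4 | (5, ∞) | (3, ∞) | terminate; footnote permits delay |

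The rows join AST/ALT and bilirubin with and/or, so either alone places a subject in a row. In the Grade 1 row the 1.5 × ULN ceiling belongs to bilirubin.

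**Step 2. AST/ALT overlaps.**

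- Grade 1 ∩ Grade 2 = (3, 5], which is all of Grade 2.
- Grade 1 ∩ Grade 3-4 = (5, ∞), which is all of Grade 3-4.
- Grade 2 ∩ Grade 3-4 is empty.
- Grade 2 ∪ Grade 3-4 = (3, ∞), which equals Grade 1. No AST/ALT value belongs to Grade 1 alone.
- All three rows together cover only (3, ∞), so (1, 3] with normal bilirubin falls in no row.

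**Step 3. Example AST/ALT values, bilirubin normal.**

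| AST/ALT (× ULN) | Rows met | Instructions |
|---|---|---|
| 2.5 | none | none |
| 3.0 | none | none |
| 4 | Grade 1, Grade 2 | continue; delay |
| 5 | Grade 1, Grade 2 | continue; delay |
| 8 | Grade 1, Grade 3-4 | continue; terminate (footnote: may delay) |
| 10 | Grade 1, Grade 3-4 | continue; terminate |

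**Step 4. Bilirubin.** The intervals (1, 1.5], (1.5, 3] and (3, ∞) meet without gap or overlap. A value of 1.2 falls in Grade 1 only, 1.6 in Grade 2 only, and 3.1 in Grade 3-4 only.

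**Step 5. Appendix 7.3 against Table 4.**

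- At Grade 2 they agree: delay in one, interrupt in the other.
- At Grade 3-4 they differ. Table 4 lists only discontinuation. The footnote allows delay for any Grade 3-4 case with AST/ALT ≤ 8 and TBIL ≤ 5 × ULN. With normal bilirubin that is AST/ALT in (5, 8].

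**The case against.** The strongest reply is that Table 4 is the operative rule and has no overlap. It works by grade, the protocol names CTCAE v4.03 as the source of grades, and the appendix column cites CTCAE v4. A site that grades by CTCAE and then applies Table 4 reaches one action, which at Grade 2 agrees with the appendix. Appendix 7 is offered as reference, lets investigators choose their own regimens, and ties its continue, delay and terminate instructions to the study protocol. Section 10.1.6.1 requires consultation with the sponsor before interrupting or resuming SHR-1210 other than as Table 4 recommends. The gap up to 3 × ULN changes little: Table 4 triggers no interruption below Grade 2, and the Grade 1 row says continue.

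Most of this stands, and it limits how often the misprint could mislead. It does not remove the contradiction. Table 4 carries no × ULN limits, and the main text sends the reader to Appendix 7, which refers back to the protocol. The appendix does not say that the highest row met governs. If it did, no AST/ALT value would ever be handled as Grade 1. Nor does the reply address the footnote.

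Three stronger inferences are tempting, and the documents do not support them:

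- **That a binding stopping rule has failed.** The appendix is reference material, and Table 4 stands beside it.
- **That 21.7% and 18.6% measure the subjects affected.** Section 5.3 gives no split of these events by grade, so the number with AST/ALT above 3 × ULN is unknown.
- **That dose-interruption data or PFS would be distorted.** SAP Section 5.5.2 grades adverse events by CTCAE v4.03 and summarises those leading to interruption or discontinuation. Nothing shows that these tables, or IRC-assessed PFS, would change.

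**Conclusion.** The point holds as an internal contradiction in safety guidance. As printed, every AST/ALT value above 3 × ULN meets two rows with opposing instructions, and every value above ULN up to 3 × ULN with normal bilirubin meets none. Bilirubin is unaffected. Separately, the footnote and Table 4 disagree for part of Grade 3-4.

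The contiguous bilirubin limits suggest a drafting or translation slip in the AST/ALT limits, not a deliberate choice. The size is given as intervals, because the documents do not allow a count of subjects. The conclusion assumes that the comparison signs were read correctly from the PDF. A misread sign cannot be wholly excluded, but the same Grade 1 cell does print an upper-limit sign for bilirubin. The correction is worth making because it is cheap and concerns subject safety. It does not bear on the validity of the primary analysis.

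**What to change.** Reconcile the three rows and the footnote of Appendix 7.3 with each other, with the liver row of Table 4 and with the CTCAE version named in the protocol. Each AST/ALT and bilirubin value should then fall in exactly one row with one instruction, and recovery to Grade 1 should have one meaning. It would also help to state which text governs if Table 4 and Appendix 7 differ. Which limits and actions apply is for the sponsor's clinicians; none is proposed here.

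The cost is appendix wording, plus any matching change in Table 4. It needs no change to the sample size or the statistical analysis.

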Type I diabetes mellitus (new onset) or hyperglycemia	New-onset type I diabetes mellitus or Grade 3-4 hyperglycemia accompanied with evidence of β -cell depletion	After clinical and metabolic conditions are stabilized	Continue SHR-1210 treatment.
Renal Failure or Nephritis	2	Recovered to Grade 0-1	Fail to resolve within 12 weeks from the last dose, or the dose of corticosteroids cannot be reduced to ≤ 10 mg of prednisone or equivalent within 12 weeks.
	3-4	Discontinuation	Discontinuation
Infusion reactions	2	Symptoms disappeared	Re-administer at 50% of the initial rate after symptoms resolve. If no reaction occurs within 30 min, restore the original infusion rate (100%). Closely monitor. If the symptoms recur, the administration of the current SHR-1210 dose will be discontinued.
	3-4	Discontinuation	Discontinuation
Other Treatment-Related Adverse Events	3	Recovered to Grade 0-1	Fail to resolve within 12 weeks from the last dose, or the dose of corticosteroids cannot be reduced to ≤ 10 mg of prednisone or equivalent within 12 weeks.
	4	Discontinuation	Discontinuation

Note: Treatment should be discontinued if any Grade 3 treatment-related AE recurs or any life-threatening event occurs.

For subjects with metastasis to liver and Grade 2 AST or ALT increased at baseline, treatment should be discontinued if a $\geq 50\%$ increase in AST or ALT from baseline persists for at least 1 week.

For subjects with intolerable or persistent Grade 2 treatment-related AEs, the investigator may consider interrupting SHR-1210 treatment if appropriate. For subjects with persistent Grade 2 adverse drug reactions that fail to recover to Grade 0-1 within 12 weeks after the last dose, the treatment should be discontinued.

For subjects with hypertension with a blood pressure not more than 140/90 mmHg whose AE is considered as Grade 3-4 only because of the administration of multiple antihypertensive drugs, treatment interruption is not required.

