Appendix 7. Management Principles for Immune Related Adverse Events

The principles specified in this section can be used as reference for the investigator when managing immune-related AEs. Investigators can select their own dosing regimens according to clinical reality.

The general principle is that AEs should be carefully evaluated and the differential diagnosis be made in accordance with the standard medical practice. Non-inflammatory causes should be considered and properly handled.

Corticosteroids are preferable drug for immuno-oncology treatment-related AEs. An oral dose equivalent to the recommended IV dose can be considered for ambulatory patients with low grade toxicity. The low bioavailability of oral administration should be taken into account when switching to the equivalent dose of oral corticosteroids.

Consultation with an internist or surgeon is recommended, especially before an invasive diagnostic or therapeutic procedure.

The frequency and severity of related adverse events included in these protocols will depend on the cancer immunotherapy or regimen being used.

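### Appendix 7.3 lets SHR-1210 be delayed for some Grade 3-4 liver events that Table 4 discontinues, without mentioning the required sponsor consultation

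*Protocol*

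**What the plan says.** - **Table 4 (Protocol 10.1.6.1).** The row "AST, ALT, or bilirubin increased" interrupts SHR-1210 at Grade 2, with resumption on recovery to Grade 0-1. At Grade 3-4 both the resumption and the discontinuation columns say to discontinue, with no exception by multiple of ULN. The table's first column limits it to treatment-related immune-related events.
- **Departures from Table 4 (same section).** "the investigator must consult with the sponsor if, based on the benefit to risk ratio of the subject, SHR-1210 should be interrupted or resumed" in a way other than Table 4 recommends, or where the situation is not listed.
- **Note under Table 4.** "For subjects with metastasis to liver and Grade 2 AST or ALT increased at baseline, treatment should be discontinued" if a rise of at least 50% over baseline lasts a week or more.
- **Appendix 7.3.** Grade 3-4 is defined as ALT/AST above 5 × ULN and/or TBIL above 3 × ULN. The first handling step is to terminate as the protocol directs, and it carries an asterisk. The footnote reads "If AST/ALT ≤ 8 × ULN and TBIL ≤ 5 × ULN, the immunotherapy can be delayed rather than discontinued".
- **Status of Appendix 7.** It opens with "The principles specified in this section can be used as reference for the investigator when managing immune-related AEs", whereas Protocol 10.1.6.2.1 sends investigators to it for safety management rules.
- **Appendix 7.1 (diarrhea/colitis).** The rows are Grade 1, Grade 2-3 and Grade 4. The Grade 1 follow-up says "Provide treatment according to the method for grade 2 or grade 3/4 situations" if the event worsens. The Grade 2-3 follow-up says "Provide treatment according to the method for grade 3/4 situations" if it worsens or persists on oral steroids. The Grade 4 row begins "Terminate the immunotherapy according to the study protocol".

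**The concern.** A site managing an immune-related Grade 3 liver event finds two instructions in one protocol. The dose-modification table says to stop SHR-1210 for good. The appendix, to which the treatment section refers, says the drug may be held instead. The footnote qualifies the very step that defers to the protocol, so that deference does not settle the matter by itself. The footnote also grants the departure without naming the sponsor consultation that 10.1.6.1 makes mandatory.

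What is at stake is a hepatic safety decision on one of the two drugs in the investigational combination, and consistency between sites in making it. The SAP's tables of adverse events leading to interruption or discontinuation (SAP 5.5.2) would depend in part on which text a site had followed. The row references in Appendix 7.1 are a lesser fault of the same kind: they point to a row that does not exist.

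**Working it through.** The plan states no figure to reproduce. The check sets the texts side by side.

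**1. Inputs.** Table 4 works in grades. Appendix 7.3 supplies the ULN limits: Grade 2 is AST/ALT > 3 to ≤ 5 and/or TBIL > 1.5 to ≤ 3 × ULN; Grade 3-4 is AST/ALT > 5 and/or TBIL > 3 × ULN. The footnote needs AST/ALT ≤ 8 and TBIL ≤ 5 × ULN together.

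**2. Zone of conflict.** This is where the Grade 3-4 definition and the footnote condition both hold, for a treatment-related immune-related event.

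| Values (× ULN) | Table 4 row | Appendix 7.3 with footnote | Agree? |
|---|---|---|---|
| Grade 2 | interrupt | delay | yes |
| AST/ALT > 5 to ≤ 8, TBIL ≤ 5 | discontinue | delay allowed | no |
| TBIL > 3 to ≤ 5, AST/ALT ≤ 8 | discontinue | delay allowed | no |
| AST/ALT > 8 or TBIL > 5 | discontinue | terminate | yes |

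**3. Subjects with liver metastasis and Grade 2 AST/ALT at baseline.** The note under Table 4 gives them a trigger of 1.5 × baseline b, sustained for at least a week. Counting only values where both the row and the note stop the drug, the AST/ALT conflict runs from max(5, 1.5b) to 8 × ULN. The baselines are illustrative, chosen within > 3 to ≤ 5 × ULN:

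| b | 1.5b | Conflict range | Width |
|---|---|---|---|
| 3.33 | 5.00 | 5.00 to 8 | 3.00 |
| 4.0 | 6.00 | 6.00 to 8 | 2.00 |
| 4.5 | 6.75 | 6.75 to 8 | 1.25 |
| 5.0 | 7.50 | 7.50 to 8 | 0.50 |

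The conflict narrows with rising baseline but does not close.

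**4. Two cases.**
- Normal baseline, AST 6 × ULN, normal bilirubin, judged treatment-related and immune-related: Table 4 discontinues SHR-1210, and apatinib alone may continue if well tolerated. The footnote allows a delay.
- Normal baseline, AST 6 × ULN, TBIL 4 × ULN, ALP ≤ 2 × ULN, no hemolysis and no other cause: this meets the potential drug-induced liver injury definition in Protocol 13.2.4 and is reported as an SAE. If it is also judged immune-related, it still lies inside the footnote's limits.

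**5. Frequency.** Protocol 5.3 reports treatment-related AST increase in 21.7% and ALT increase in 18.6% of 258 subjects (about 56 and 48), without grades and without the immune-related share. The number in the conflict zone cannot be derived.

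**6. Appendix 7.1.** Row labels are {1, 2-3, 4}; the references are to {2 or 3/4} and {3/4}. No row is labelled 3/4, and Grade 3 sits with Grade 2. The same wording in Appendices 7.2 and 7.3 does match rows there, so the fault is confined to 7.1. For a Grade 2-3 event persisting on oral steroids, it is unclear whether the Grade 4 steps apply (methylprednisolone 1.0-2.0 instead of 0.5-1.0 mg/kg/d, then infliximab). On stopping the drug, 7.1 otherwise agrees with Table 4: hold at Grade 2-3, discontinue at Grade 4.

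**The case against.** The case for leaving the text alone is that precedence is nearly settled. Appendix 7 calls itself reference material, its liver row defers to the protocol, and 10.1.6.1 already permits holding and resuming SHR-1210 against Table 4 after consultation. The footnote is permissive and does not waive that consultation. A site that applies Table 4 and consults the sponsor is unaffected.

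Other safeguards exist. Grade ≥ 3 immune-related events reach the sponsor within 24 hours as events of special interest (Protocol 13.4), and the notes under Table 4 stop treatment if a Grade 3 treatment-related event recurs. These points stand and limit the weight of the finding. They do not remove the conflict: notification is not consultation, 10.1.6.2.1 presents the same appendix as rules, and no sentence ranks the two texts.

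A reader might infer four stronger things that the documents do not support.
- *Every rise above 5 × ULN must stop SHR-1210.* Table 4 covers treatment-related immune-related events. Appendix 7.3 continues immunotherapy when the cause is non-inflammatory, and 10.1.6.3 handles apatinib-related Grade ≥ 3 toxicity by delaying apatinib.
- *The footnote is the erroneous text.* Its thresholds are specific and may be intended. Nothing says which text should yield.
- *A restart could pass unnoticed.* The 24-hour report makes that less likely.
- *Appendix 7.1 orders a permanent stop for persisting Grade 2-3 colitis.* The reference concerns how to treat the event, and the Grade 4 row's stop is itself subject to the protocol, which leads back to Table 4. The Grade 1 reference is resolved by using the row for the grade reached.

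**Conclusion.** The inconsistency is real and worth correcting. For treatment-related immune-related liver events, Table 4 discontinues SHR-1210 while the Appendix 7.3 footnote allows a delay, across the two ranges in the working. The footnote is silent on the consultation that such a departure requires.

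This rests on two readings: that the ULN limits in Appendix 7.3 are the ones meant by the grades in Table 4, and that the event is attributed to treatment and judged immune-related. The number of subjects affected is unknown. Sample size, alpha and the primary test are unaffected; PFS in SAP 4.1.1.1 counts progression whether or not treatment continues. The Appendix 7.1 references are mainly a labelling fault and carry less weight.

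**What to change.** 1. **Appendix 7.3 footnote.** Allow the delay *only after the sponsor consultation required in 10.1.6.1*, or delete the footnote and its asterisk. If the sponsor intends the thresholds as a standing exception, they belong in Table 4.
2. **Protocol 10.1.6.1.** Add: *Where Table 4 and Appendix 7 differ on SHR-1210 interruption, resumption or discontinuation, Table 4 governs; departures, and situations not listed in Table 4, follow the sponsor consultation above. The Appendix 7.2 Grade 1 pneumonitis and Appendix 7.4 suspected adrenal crisis instructions remain in force.* The last sentence protects instructions that have no counterpart in Table 4.
3. **Appendix 7.1 (minor).** Relabel the two references to match the Grade 2-3 and Grade 4 rows, and state that interruption and discontinuation of SHR-1210 for colitis follow Table 4. Which medical escalation steps apply to persisting Grade 2-3 colitis, infliximab included, is for the sponsor's clinicians to decide; the documents do not settle it.

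Cost: a protocol amendment, which needs ethics committee approval before use (Protocol 18.3), and a memo to the approximately 30 sites. Data collection, sample size and analysis do not change.
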